6.3.1 Potential drug-induced liver injury IMP discontinuation criteria

Subjects with potential drug-induced liver injury (PDILI) must be assessed to determine if investigational medicinal product (IMP) must be immediately and permanently discontinued. In addition, all concomitant medications and herbal supplements that are not medically necessary should also be discontinued.

The PDILI criteria below require immediate and permanent discontinuation of IMP:

- Subjects with either of the following:
 - ALT or AST $\geq 5 \times \text{ULN}$
 - ALT or AST $\geq 3 \times \text{ULN}$ and coexisting total bilirubin $\geq 2 \times \text{ULN}$

The PDILI criterion below requires immediate discontinuation of IMP:

- Subjects with ALT or AST $\geq 3 \times \text{ULN}$ who exhibit temporally associated symptoms of hepatitis or hypersensitivity. Hepatitis symptoms include fatigue, nausea, vomiting, right upper quadrant pain or tenderness. Hypersensitivity symptoms include fever (without clear alternative cause), rash, or eosinophilia (ie, $>5\%$).

The PDILI criterion below allows for subjects to continue on IMP at the discretion of the investigator.

- Subjects with ALT or AST $\geq 3 \times \text{ULN}$ (and $\geq 2 \times$ Baseline), and $< 5 \times \text{ULN}$, total bilirubin $< 2 \times \text{ULN}$, and no eosinophilia (ie, $\leq 5\%$), with no fever, rash, or symptoms of hepatitis (eg, fatigue, nausea, vomiting, right upper quadrant pain or tenderness)

Evaluation of PDILI must be initiated as described in Section 10.6.1. If subjects are unable to comply with the applicable monitoring schedule, IMP must be discontinued immediately.

Investigators should attempt to obtain information on subjects in the case of IMP discontinuation to complete the final evaluation. Subjects with PDILI should not be withdrawn from the study until investigation and monitoring are complete. All results of these evaluations and observations, as well as the reason(s) for IMP discontinuation and subject withdrawal (if applicable), must be recorded in the source documents. The eCRF must document the primary reason for IMP discontinuation.

7 STUDY TREATMENT(S)

7.1 Description of investigational medicinal product

Investigational medicinal product (IMP) will be provided as LCM oral solution (LCM 10mg/mL) and LCM tablets (LCM 50mg and LCM 100mg).

The oral solution formulation contains 10mg/mL of drug substance and is colorless to pale yellow in appearance.

The tablet formulation will be supplied in doses of 50mg and 100mg. The 50mg tablets are light pink, oval, film-coated tablets debossed with "SP" on one side and "50" on the other. The 100mg tablets are dark yellow, oval, film-coated tablets debossed with "SP" on one side and "100" on the other.

7.2 Treatment(s) to be administered

Lacosamide will be administered bid (at approximately 12-hour intervals, once in the morning and once in the evening) in divided doses. The oral solution formulation will be measured and administered via a dosing syringe.

Oral administration is the preferred route in this study. Feeding tube administration is an alternative route in case a subject is unable to swallow the study medication.

Each subject's weight will be monitored at every visit, and the LCM dose will be adjusted accordingly.

7.2.1 Treatment Period

After completion of the Transition Period in the primary study, all subjects will have been transitioned to a dose of LCM according to their weight. Subjects will receive LCM 10mg/kg/day (oral solution) for subjects weighing <30kg, LCM 6mg/kg/day (oral solution) for subjects weighing ≥30kg to <50kg, and LCM 300mg/day (tablets) for subjects weighing ≥50kg during at least their first week in the Treatment Period of EP0034. After 1 week in EP0034, the investigator may adjust the LCM dose during the Treatment Period based on clinical judgment according to Table 7-1. If the investigator wants to adjust the LCM dosage after 1 week in EP0034, the subject should return to the clinic for an Unscheduled Visit, at the discretion of the investigator. Subjects who are able and willing to swallow tablets may be dispensed LCM tablets during the Treatment Period, based on clinical judgment, regardless of weight. Lacosamide doses may be increased up to a maximum of LCM 600mg/day or 12mg/kg/day, whichever is lower based on body weight.

Table 7-1: Minimum and maximum LCM dose during the Treatment Period

Formulation	Minimum LCM dose	Maximum LCM dose
Oral solution	2mg/kg/day	12mg/kg/day
Tablets	100mg/day	600mg/day

LCM=lacosamide

Subjects may be allowed to switch from one formulation to the other formulation during the Treatment Period based on clinical judgment. Consideration of the current LCM milligram dose in the oral solution should occur if/when transitioning to the tablet formulation. In cases where the LCM dose received with the oral solution is not supported by the tablet strengths available in EP0034 (50mg and 100mg), a clinical decision must be made by the investigator or other study physician to either increase or decrease the LCM dose to the next multiple of 50mg with a maximum permitted dose of 600mg/day.

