1 SUMMARY

EP0034 is a Phase 3, multicenter, open-label, extension study to obtain long-term safety and efficacy data in pediatric subjects with epilepsy with partial-onset seizures treated with lacosamide (LCM) oral solution or LCM tablets as adjunctive therapy. The study will provide continued availability of LCM to subjects who have completed SP0969 (pediatric subjects with epilepsy aged ≥ 4 to < 17 years with partial-onset seizures). EP0034 will also be open to subjects who participate in SP0967 (pediatric subjects with epilepsy aged 1 month to < 4 years with partial-onset seizures). Both SP0969 and SP0967 are Phase 3, double-blind, placebo-controlled studies for LCM as adjunctive therapy.

Approximately 500 subjects from SP0967 and SP0969 may be eligible to enroll in this open-label extension study, for a maximum duration per subject of approximately 2 years. The number of sites is dependent on the number of enrolling centers from SP0967 and SP0969. The study will be conducted in North America, Europe, Latin America, and the Asia/Pacific regions, with the possibility to expand the study to other countries and regions if deemed necessary. At selected sites, subjects may also be able to participate in a substudy without withdrawing from EP0034.

The study medication is LCM in either the oral solution formulation or tablet formulation. Subjects may take either oral solution or tablets during the Treatment Period, based on clinical judgment, regardless of their weight. Lacosamide will be administered twice daily (bid) at approximately 12-hour intervals, once in the morning and once in the evening, in divided doses. The oral solution formulation will be measured and administered via a dosing syringe.

After completion of the Transition Period in the primary study, subjects will have been transitioned to a dose of LCM according to their weight. Subjects will receive LCM 10mg/kg/day (oral solution) for subjects weighing < 30 kg, LCM 6mg/kg/day (oral solution) for subjects weighing ≥ 30 kg to < 50 kg, and LCM 300mg/day (tablets) for subjects weighing ≥ 50 kg during at least their first week in the Treatment Period of EP0034. After 1 week in EP0034, the investigator may adjust the LCM dose during the Treatment Period based on clinical judgment within a range of 2mg/kg/day to 12mg/kg/day for the oral solution and 100mg/day to 600mg/day for the tablets.

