8.1.3 Visit 2 (Week 4)

At Visit 2 (end of Week 4 \pm 7 days relative to Visit 1), subjects will return for a clinic visit and the following will be performed:

- Concomitant medications assessment
- Concomitant AEDs assessment
- VNS assessment (if applicable)
- Physical examination (brief)
- Blood pressure and pulse rate, including orthostatic assessments in ambulatory subjects
- Body weight and height assessments
- Neurological examination (brief)
- 12-lead ECG (2 interpretable recordings, approximately 20 to 30 minutes apart, to be performed prior to vital signs assessment and, if possible, after the subject has been in a supine position for approximately 5 minutes preceding the ECG recording)
- Urine pregnancy test (for female subjects of childbearing potential)
- C-SSRS (for all subjects \geq 6 years of age, the "Since Last Visit" version should be completed; if a subject becomes 6 years of age during the study, the "Already Enrolled" version should be used at the first visit at which the subject is 6 years of age and the "Since Last Visit" version at subsequent visits)
- Contact IXRS
- Review LCM return and compliance
- Dispense LCM (the investigator may adjust the LCM dose according to Table 7-1)
- Reminder to complete subject diary on a daily basis
- Review withdrawal criteria
- Adverse event reporting
- Health care resource use

A telephone contact will be made approximately 2 weeks after Visit 2 (end of Week 6, Section 8.1.2). Subjects will be scheduled to return to the clinic for the next visit in approximately 4 weeks.

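### The lower-of cap on lacosamide dose (600 mg/day or 12 mg/kg/day) is not carried into Table 7-1, the Summary range or the formulation-switch rule, and the switch rule permits doses that the cap bars

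*Protocol*

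**What the plan says.** **The joint cap.** Protocol 7.2.1 states in its text: "Lacosamide doses may be increased up to a maximum of LCM 600mg/day or 12mg/kg/day, whichever is lower based on body weight". The same sentence stands in the dose rationale (Protocol 5.4), and SAP 2.3 repeats the limit in its account of the Treatment Period.

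**The ceilings by formulation.** Table 7-1, in the same Section 7.2.1, gives minimum and maximum as "Oral solution 2mg/kg/day 12mg/kg/day" and "Tablets 100mg/day 600mg/day". The tablet row has no mg/kg limit and the solution row has no mg/day limit. The Summary states the permitted adjustment in the same way: "within a range of 2mg/kg/day to 12mg/kg/day for the oral solution and 100mg/day to 600mg/day for the tablets".

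**The switch rule.** When a solution dose cannot be made up from 50 mg and 100 mg tablets, Protocol 7.2.1 has the physician move the dose up or down "to the next multiple of 50mg with a maximum permitted dose of 600mg/day". No mg/kg limit is attached.

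**Who may take tablets.** The Summary says: "Subjects may take either oral solution or tablets during the Treatment Period, based on clinical judgment, regardless of their weight". Sections 5.1, 7.2.1 and 8.1.1 say the same in substance.

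**Where dose is adjusted.** At Visit 2 the instruction is that "the investigator may adjust the LCM dose according to Table 7-1". Section 8.1.1 and the later dispensing visits through Week 84 point to the same table. None of them repeats the joint cap. Section 5.1 cites Table 7-1 and also refers the reader to Section 7.2.1.

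**The concern.** The maximum dose is a safety limit in a pediatric study whose primary objective is long-term safety and tolerability. Some passages state it as a joint limit, and others state it as two separate limits that depend only on formulation. The places a site would use when adjusting or switching (the table, the Summary, the switch rule and the visit bullets) are the ones that lack the joint cap.

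Two things are at stake. First, a site that works from the table, the Summary or the switch rule could go above the limit in the text while following the passage in front of it. Second, SAP 3.4 has a deviation category for the lacosamide dosing regimen, and SAP Section 7 evaluates dosing compliance only through that category. If the governing limit is not settled, the same dose can be a deviation under one passage and allowed under another.

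There is also a smaller reporting issue. The highest modal-dose category in SAP 3.2.8 is open-ended from 12 mg/kg/day, so a child exactly at the joint cap and a child above it fall in the same column of that table.

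**Working it through.** The plan gives no worked figure to reproduce, and no sample size or error rate is involved. The check compares the stated limits at given body weights.

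**Inputs**
- Joint cap (Protocol 7.2.1 text, Protocol 5.4, SAP 2.3): min(600, 12 × kg) mg/day.
- Tablet ceiling (Table 7-1, Summary): 600 mg/day.
- Solution ceiling (Table 7-1, Summary): 12 × kg mg/day.
- Switch rule, rounding up from the solution maximum (Protocol 7.2.1): 12 × kg raised to the next multiple of 50 mg, ceiling 600 mg/day.

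**Step 1: where the limits meet.** 600 / 12 = 50 kg. Below 50 kg the mg/kg limit is the lower one; above 50 kg the mg/day limit is.

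**Step 2: switch rule, rounding up from 12 mg/kg/day**

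| Weight | Joint cap | Rounded up | mg/kg/day |
|---|---|---|---|
| 20 kg | 240 mg | 250 mg | 250/20 = 12.5 |
| 30 kg | 360 mg | 400 mg | 400/30 = 13.3 |
| 40 kg | 480 mg | 500 mg | 500/40 = 12.5 |

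The child need not be exactly at the solution maximum. The largest 50 mg multiple within the joint cap is 200 mg at 20 kg (10 mg/kg/day), 350 mg at 30 kg (11.7) and 450 mg at 40 kg (11.25). Rounding up from any solution dose above that multiple exceeds the cap. At weights where 12 × kg is itself a multiple of 50 (25 kg, 300 mg), rounding up cannot exceed it.

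**Step 3: tablet row of Table 7-1 read alone, below 50 kg**
- 45 kg: 600 against 540 mg/day, 600/45 = 13.3 mg/kg/day.
- 40 kg: 600 against 480 mg/day, 600/40 = 15 mg/kg/day.
- 30 kg: 600 against 360 mg/day, 600/30 = 20 mg/kg/day.

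At 50 kg and above the tablet row and the joint cap agree.

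**Step 4: solution row of Table 7-1 read alone, above 50 kg**
- 60 kg: 12 × 60 = 720 mg/day against 600.
- 70 kg: 12 × 70 = 840 mg/day against 600.

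**Step 5: the lower end.** The tablet minimum of 100 mg/day exceeds 12 mg/kg/day below 100/12 = 8.3 kg. Few children of that weight would take tablets, so this is a gap in the wording more than a likely exposure.

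**The case against.** The best answer is that the passages can be read together. The lower-of sentence stands directly above Table 7-1 in the same section, Section 5.1 sends the reader to that section, and any dose under the joint cap also satisfies the table and the Summary. SAP 2.3 reads them this way: it cites Table 7-1 for adjustment and then states the joint maximum. Section 7.2 also requires weight to be checked at every visit and the dose adjusted. The switch rule permits rounding down as well as up, so it can be followed within the cap.

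Much of this stands, and it rules out several stronger readings that a reader might infer:

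- *That the rules cannot both be obeyed, or that the table grants 600 mg/day at any weight.* The table is silent on weight. The phrase has to be inferred from the missing mg/kg limit and a separate sentence on choice of formulation.
- *That children will be taken to 20 or 30 mg/kg/day.* Such figures (600 mg/day at 30 or 20 kg) need a site to ignore the sentence next to the table. Children under 30 kg start on solution at 10 mg/kg/day, and the switch rule starts from the current milligram dose.
- *That safety is being described at doses the cap forbids.* Nothing in the documents shows that such doses were given. SAP 3.2.8 converts tablet doses to mg/kg/day and summarises the maximum daily dose as a continuous variable, so they would show there.
- *That dosing deviations cannot be classified consistently.* SAP 3.4 puts the criteria in a separate document that is not available here and asks for algorithmic application where possible.

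What the objection does not remove is the switch rule. It follows the table, states its own ceiling, and expressly permits an upward step that the cap bars at many weights. Nor does it explain why the Summary and the visit sections leave the cap out.

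**Conclusion.** The inconsistency is real. It is one of wording: a joint cap that three places state and three others omit. The firmest conflict is the switch rule, where rounding up yields about 12.5 to 13.3 mg/kg/day at the 20, 30 and 40 kg examples against a cap of 12. The wider gaps, 15 mg/kg/day on tablets at 40 kg and 720 mg/day on solution at 60 kg, arise only if the table or Summary is read without the adjacent text. Tablets at 50 kg or more, and solution at 50 kg or less, are unaffected.

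This rests on two assumptions: that tablets are in fact used below 50 kg or solution above it, as the protocol allows, and that some sites work from the table, Summary or switch rule without the 7.2.1 sentence. The documents show neither how often this would happen nor that any over-cap dose was given. The correction is still warranted, because the limit concerns children's safety and is cheap to state once.

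**What to change.** Reconcile four places so that they state the same limit by weight and formulation: Table 7-1, the Summary range, the formulation-switch rule and the lower-of sentence in Protocol 7.2.1 (with its copies in Protocol 5.4 and SAP 2.3). The switch rule should say explicitly whether upward rounding is bounded by a mg/kg limit as well as by 600 mg/day. Carry the reconciled limit to the Table 7-1 cross-references in Section 5.1 and the visit sections. Code deviations in the dosing-regimen category of SAP 3.4 against that single rule. Which maximum is right is for the sponsor to settle and is not judged here.

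Cost: a protocol wording amendment, a clarification to sites, matching text in SAP 2.3 if it changes, and a check of the important protocol deviations document. No new visits, assessments or procedures are needed.

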7.2.2 Taper Period

Subjects who withdraw during the study should taper off LCM if the following doses are achieved: LCM \geq 3mg/kg/day for subjects receiving LCM oral solution or LCM \geq 150mg/day for subjects taking tablets. It is recommended that the dose be tapered gradually in weekly decrements (see [Table 7-2](#) and [Table 7-3](#)). A slower taper is permitted, if medically necessary. In case of an emergency, a faster taper is permitted after discussion with the Medical Monitor, whenever possible.

Table 7-2: Dose taper steps for subjects receiving oral solution

LCM dose achieved	LCM doses for the Taper Period				
	Week 1	Week 2	Week 3	Week 4	Week 5
11 to 12mg/kg/day	9mg/kg/day	6mg/kg/day	4mg/kg/day	2mg/kg/day	–
9 to 10mg/kg/day	8mg/kg/day	6mg/kg/day	4mg/kg/day	2mg/kg/day	–
7 to 8mg/kg/day	6mg/kg/day	4mg/kg/day	2mg/kg/day	2mg/kg/day	–
5 to 6mg/kg/day	4mg/kg/day	2mg/kg/day	2mg/kg/day	–	–
3 to 4mg/kg/day	2mg/kg/day	2mg/kg/day	–	–	–

LCM=lacosamide

Table 7-3: Dose taper steps for subjects taking tablets

LCM dose achieved	LCM doses for the Taper Period				
	Week 1	Week 2	Week 3	Week 4	Week 5
>500 to 600mg/day	500mg/day	300mg/day	200mg/day	100mg/day	–
>400 to 500mg/day	400mg/day	300mg/day	200mg/day	100mg/day	–
>300 to 400mg/day	300mg/day	200mg/day	100mg/day	100mg/day	–
>200 to 300mg/day	200mg/day	100mg/day	100mg/day	–	–
≥150 to 200mg/day	100mg/day	100mg/day	–	–	–

LCM=lacosamide

Taper of LCM may not be required for some subjects who complete the study or withdraw from the study prematurely, depending on the treatment option selected by the investigator in consultation with the subject and/or legal representative(s) or for subjects who participate in EP0151 or EP0152.

7.2.3 Alternative study treatment supply due to coronavirus disease 2019 pandemic

When a subject can no longer return to the study site due to general circumstances but will continue in the study, the following methods may be used to provide study treatment:

- Site to subject: In instances where site staff can ship study treatment dispensed from the site pharmacy supply directly to the subject.
- Depot to subject: In instances where it is not possible for the site staff to access study treatment in the site pharmacy and/or ship study treatment dispensed from the site pharmacy supply directly to the subject.

7.3 Packaging

Lacosamide (tablets and oral solution) is manufactured, packaged, and labeled according to Good Manufacturing Practice (GMP) guidelines and applicable laws or regulations. The IMP is suitably packaged in such a way as to protect the IMP from deterioration during transport and storage.

Lacosamide 10mg/mL oral solution will be packaged in amber polyethylene terephthalate bottles with a white, child-proof, polypropylene screw cap. The LCM dose will be measured and administered via a dosing syringe.

Lacosamide tablets will be packaged in high-density polyethylene bottles with a child-proof, polypropylene screw cap.

7.4 Labeling

Clinical drug supplies will be labeled in accordance with the current ICH guidelines on Good Clinical Practice (GCP) and GMP and will include any locally required statements. If necessary, labels will be translated into the local language.

7.5 Handling and storage requirements

Lacosamide is to be stored according to the instructions on the label.

The investigator (or designee) is responsible for the safe and proper storage of IMP at the site. Investigational medicinal product stored by the investigator is to be kept in a secured area with limited access.

Appropriate storage conditions must be ensured either by controlled room temperature or by completion of a temperature log in accordance with local requirements on a regular basis, showing minimum and maximum temperatures reached over the time interval.

In case an out-of-range temperature is noted, it must be immediately communicated to the sponsor's designee in accordance with the pharmacy manual.

The investigator (or designee) will instruct the subject to store the IMP following the instructions on the label.

7.6 Drug accountability

A Drug Accountability form will be used to record IMP dispensing and return information on a by-subject basis and will serve as source documentation during the course of the study. Details of any IMP lost (due to breakage or wastage), not used, disposed of at the study site, or returned to the sponsor's designee must also be recorded on the appropriate forms. All supplies and pharmacy documentation must be made available throughout the study for UCB (or designee) to review.

The investigator (or designee) is responsible for retaining all used, unused, and partially used containers of IMP until returned.

The investigator may assign some of the investigator's duties for drug accountability at the study site to an appropriate pharmacist/designee.

The investigator must ensure that the IMP is used only in accordance with the protocol.

Periodically, and/or after completion of the clinical phase of the study, all used (including empty containers) and unused IMP containers must be reconciled and returned to UCB's designee, preferably in their original package. The IMP intended for the study cannot be used for any other purpose than that described in this protocol.

7.7 Procedures for monitoring subject compliance

At each visit after IMP is dispensed, subjects must return all used, unused, and empty IMP containers. Drug accountability must be done in the subject's presence in order to obtain explanations regarding discrepancies in compliance with the dosing regimen. Drug accountability must be recorded on the Drug Accountability form.

If a subject is found to be persistently noncompliant (defined as less than 75% or more than 125% compliant with the dosage schedule), the sponsor, in conjunction with the investigator, will make a decision as to whether the subject should be withdrawn from the study.

Timely completion of the subject diary is essential for evaluation of safety and efficacy. Subject diary use will be confirmed at each visit and telephone contact.

7.8 Concomitant medication(s)/treatment(s)

7.8.1 Permitted and prohibited concomitant treatments (medications and therapies)

All concomitant medication and treatment must be recorded in the appropriate study documents (ie, eCRF and source document).

The following concomitant medications are prohibited during the study:

- Clozapine
- Monoamine oxidase-A inhibitors
- Barbiturates (except as AEDs)
- Cannabidiols (not approved or indicated for epilepsy by local health authority)
 - Long-term use of narcotic analgesics (the use of short-term [2 to 3 weeks] narcotic analgesics may be allowed for management of acute pain (eg, fractures) or during the perioperative period for subjects requiring surgery).

Neuroleptics (except for clozapine) are allowed during the study but the investigator should make every effort to keep the dose stable.

The use of amphetamines and sedative antihistamines is allowed during the study. Also, low doses of anxiolytics or hypnotics are allowed for nonepilepsy indications.

If needed to optimize tolerability and seizure reduction in selected subjects, concomitant AEDs may be carefully tapered and discontinued to achieve LCM monotherapy. New concomitant AEDs may be introduced as treatment if the medication has been approved by the regulatory authorities in the country in which the subject lives. New concomitant AEDs should be added only when the subject has not optimally or adequately responded to a maximum tolerated dose of LCM.

Implantation of and changes in vagal nerve stimulation settings are permitted.

The investigator must contact the Medical Monitor if surgery is planned for any subject. In general, it is not necessary to discontinue LCM for subjects undergoing surgery, although each case must be discussed on a case-by-case basis. The investigator must contact the Medical Monitor before re-starting LCM after a surgery.

Therapy that becomes necessary, in the investigator's opinion, during the course of the study must not be refused to a subject, even if described above as a therapy that is expressly not permitted in the frame of this study. The subject's participation in this study may be discontinued in such a case.

